### **10.3 Pharmacodynamic Assessments**

From the Holter monitor, the PD parameters will be collected, including heart rate, QTcF, PR interval, QT interval, RR interval, and QRS interval.

The laboratory that measures the PD parameters will prepare a plan for the measurements by the time the measurements are started, and prepare a report after completion of the measurements.

## 11. Assurance of the Safety of Subjects

### 11.1 Actions to Be Taken in the Serious Adverse Events

If any SAE occurs between the start of study drug administration and the end-of-study assessment, regardless of its relationship to the study drug, the investigator (or subinvestigator) will immediately provide the subject with appropriate treatments.

All SAEs must be notified to the sponsor within 24 hours of the investigator (or subinvestigator) becoming aware of the event, using a uniform format for the SAE report with the investigator's (or subinvestigator's) name and seal or signature and the date by facsimile as the first report. The SAE report should include all available information, including the relationship to the study drug. In the SAE report, the subject must be identified via the code numbers that are assigned to each study participant, and not by the subject's name, personal ID number, or address.

The investigator will send the SAE report, along with more detailed information to the sponsor by facsimile, using a uniform format with the investigator's (or subinvestigator's) name and seal or signature and the date within 7 days after sending the first report. The investigator (or subinvestigator) will report the SAE to the monitor (in writing in principle) promptly after becoming aware of the event. The investigator (or subinvestigator) will also report detailed information to the sponsor within 7 days. In addition, the investigator will report the SAE to the head of the study site.

#### [Definitions of SAE]

- (1) Death
- (2) A case which may lead to death
- (3) A case which requires hospitalization in a hospital or clinic, or extension of a hospitalization period for treatment
- (4) Disability
- (5) A case which may lead to disability
- (6) A case of a serious disease, according to the cases listed in (1) through (5)
- (7) A congenital disease or abnormality in later generations

The following table compares the differences in the definitions of SAEs between that given above (in the Article 273 of the Enforcement Regulations of the Law on Securing Quality, Efficacy and Safety of Products Including Pharmaceuticals and Medical Devices) and those specified in Notification No. 227 of the Pharmaceuticals and Cosmetics Division, PAB and the International Council for Harmonisation of Technical Requirements for Pharmaceuticals for Human Use (ICH).

An "SAE" in Notification No. 227 of the Pharmaceuticals and Cosmetics Division, PAB and the ICH is defined as any medical condition that:	Article 273 of the Enforcement Regulations of the Law on Securing Quality, Efficacy and Safety of Products Including Pharmaceuticals and Medical Devices
Results in death;	↔ Death
Is life-threatening;	↔ A case which may lead to death
Requires inpatient hospitalization or results in prolongation of an existing hospitalization;	↔ A case which requires hospitalization in a hospital or clinic, or extension of a hospitalization period for treatment
Results in a persistent or significant disability/incapacity;	↔ Disability
Other important medical events or reactions;	↔ A case which may lead to disability
Is a congenital anomaly/birth defect.	↔ A case of a serious disease, according to the cases listed above ↔ A congenital disease or abnormality in later generations

## 11.2 Pregnancy Report

If the investigator (or subinvestigator) becomes aware of the pregnancy of a male subject's female partner, and that her embryo or fetus may be exposed to the study drug before completion of the contraception period, the investigator (or subinvestigator) shall promptly report to the sponsor using the Pregnancy Report in Appendix 1. If the female partner wishes to give birth to the child, the investigator (or subinvestigator) will follow up to her delivery, as much as possible, and assess whether or not there are any effects on the newborn. The investigator (or subinvestigator) will report the results, in detail to the sponsor using the Pregnancy Report in Appendix 1.

## 11.3 Communication to Other Hospitals and Departments Regarding the Subjects' Medical Care

Prior to the screening of each subject and during the study period, the investigator (or subinvestigator) will confirm whether the subject has received any medical care by another physician outside of the study. If he/she has received such care, the investigator (or subinvestigator) will inform the physician that the subject is participating in the study with his consent. In addition, the investigator (or subinvestigator) or study collaborator will instruct the subject to inform physicians at other hospitals or departments regarding his participation in the clinical study.

## **12. Criteria and Procedures for Subject Withdrawal**

### **12.1 Criteria for Subject Withdrawal**

A subject will be withdrawn from the study if any of the following criteria are met.

- (1) The subject requests to withdraw from the study.
- (2) The subject is determined to be clearly ineligible as a study subject.
- (3) Study continuation becomes difficult for the subject due to the onset of an AE.
- (4) Other cases where the investigator (or subinvestigator) judges that the subject should be withdrawn from the study.

[Rationales for setting]

These criteria were established to perform the study ethically and to ensure the safety of the subjects.

### **12.2 Procedures for Subject Withdrawal**

If a subject discontinues participation in the study between the start of study drug administration and the end of safety evaluation, the investigator (or subinvestigator) will take appropriate actions for the subject, and promptly report to the sponsor regarding the subject's withdrawal from the study. Within 3 days from the last dose, the investigator (or subinvestigator) will perform the tests and observations that are specified in the end-of-study assessment.

The investigator (or subinvestigator) will record the date and reason for discontinuation in the CRF. If the onset of an AE leading to the discontinuation of the subject, the investigator (or subinvestigator) will record the AE in the discontinuation section in the CRF. The date of discontinuation will be the date when the investigator (or subinvestigator) judges that the subject will be withdrawn from the study.

If the subject misses the observations and tests that are to be performed within 3 days from the last dose, or if he/she does not return to visits after discontinuation, the investigator (or subinvestigator) will make attempts to follow him/her up in order to identify the reason and subsequent course, by letter or phone, and record the results in the discontinuation section in the CRF.

## 13. Statistical Analysis

### 13.1 General Requirements

Detailed statistical analysis procedures will be documented in a separate Statistical Analysis Plan. The Statistical Analysis Plan will be prepared and fixed prior to data lock. In addition, all individual subject data will be listed.

### 13.2 Analysis Sets

The definitions of the analysis sets are provided below. The detailed handling of subjects will be determined by the sponsor, by the time of the data lock.

(1) Safety analysis set

The safety analysis set will consist of all subjects who received at least 1 dose of the study drug.

(2) PK analysis set

The PK analysis set will consist of all subjects who received at least 1 dose of the study drug and had evaluable PK data.

(3) PD analysis set

The PD analysis set will consist of all subjects who received at least 1 dose of the study drug and had evaluable PD data.

### 13.3 Data Handling

The data will be handled as described below, except for cases determined in the sponsor's case conference or at the conference for the handling of drug concentration data. The handling of the safety, drug concentration, and PD data will be specified in the Statistical Analysis Plan or the Clinical Study Report.

[1] Definition of the baseline for the safety and PD assessments

Unless otherwise specified, the baseline for these assessments is the last data measured prior to the start of study drug administration.

[2] Handling of analysis data for each time point

The acceptable time range for each measurement time point will be specified in the Statistical Analysis Plan, and the data collected within the time range will be used. Data will not be imputed by data collected outside the time range. If multiple data exist within the same time range for one assessment item, the data collected later will be used.

[3] Handling of unmeasurable data and reference data in laboratory tests

If unmeasurable or reference data are obtained due to specimen problems, they will be handled as missing data.

[4] Handling of PK data

The acceptance time range for each blood sampling timepoint for determining the plasma drug concentrations will be specified in the Statistical Analysis Plan. The sponsor will judge the handling of the following data, as to whether or not to include them in the tabulation and analysis of the drug concentrations: (1) data that was

collected from a blood specimen drawn outside of the acceptance time range; (2) data for which the plasma drug concentration was unmeasurable; and, (3) data for which a protocol deviation occurred, such as non-compliance with plasma collection procedures. The handling of data will be decided at the case conference or at the conference for the handling of PK data.

### **13.4 Statistical Analysis Plan**

Analytical variables will be classified into numerical, categorical, and ordinal data. For numerical data, descriptive statistics (number of subjects, mean, standard deviation, minimum, median, and maximum) will be calculated. For categorical and ordinal data, the frequency (%) will be calculated for each category. In the single-dose and multiple-dose studies, data collected at each dose of each cohort will be compared with the corresponding pooled data of the placebo group.

(1) Analysis of demographic characteristics and other baseline characteristics

Age, sex, height, body weight, BMI, race, medical history, complications, and concomitant medications will be listed by subject.

(2) Safety

AEs and adverse drug reactions (ADRs)

AEs will be coded using the Medical Dictionary for Regulatory Activities (MedDRA, version 20.0 or higher). AEs will be listed by subject, including such data as the timepoints of occurrence/disappearance, term used by the reporter, preferred term, system organ class (SOC), severity, seriousness, relationship to the investigational drug or comparator, and outcome. All AEs that occurred before the start of administration will be classified into baseline AEs and presented only in the list. In contrast, all AEs that occurred or became aggravated after the investigational drug or comparator administration will be classified into treatment-emergent adverse events (TEAEs), and these will be tabulated. In the tabulation, the number of subjects with TEAEs and the incidence and number of TEAEs will be summarized.

TEAEs will be tabulated, as shown below.

- Tabulation by SOC and preferred term
- Tabulation by SOC, preferred term, and severity
- Tabulation by SOC, preferred term, and relationship to the investigational drug

A list will be prepared for TEAEs leading to discontinuation of administration and serious TEAEs.

• Vital signs and laboratory tests

For vital signs (systolic and diastolic blood pressure, pulse rate, and body temperature) and laboratory data (hematology, biochemistry, coagulation test, and urinalysis), descriptive statistics will be calculated for values at each time point and changes from baseline. Urinalysis data will be listed by subject for each time point. Data outside of the reference range will be indicated via an attached flag in the list.

• 12-lead ECG

Descriptive statistics will be calculated for 12-lead ECG data, for each timepoint. Data outside of the reference range will be indicated via an attached flag in the list.

(3) Pharmacokinetics

For the plasma concentrations of unchanged edaravone, sulfate conjugate, and glucuronide conjugate, descriptive statistics will be calculated by dose for each time point and time after dosing. In addition, descriptive statistics will be calculated for the PK parameters (e.g.,  $C_{max}$ ,  $t_{max}$ , AUC, and  $t_{1/2}$ ) of unchanged edaravone, sulfate conjugate, and glucuronide conjugate by dose.

- Dose proportionality will be assessed using the  $C_{max}$ ,  $AUC_{0-\text{last}}$ , and  $AUC_{0-\infty}$  (except for Cohort S3-2) of unchanged edaravone, sulfate conjugate, and glucuronide conjugate collected in Part 1, using a power model. In addition, the linearity will be evaluated using a lack-of-fit test.
- The effect of food on the PK parameters of edaravone will be assessed using the  $C_{max}$ ,  $AUC_{0-\text{last}}$ , and  $AUC_{0-\infty}$  of unchanged edaravone, sulfate conjugate, and glucuronide conjugate in Cohorts S3-1 and S3-2. The geometric mean ratio (fed/fasting conditions) and the 90% confidence interval will be calculated via analysis of variance, using the data after log transformation under fed and fasting conditions and the subjects as factors.
- The ratio of the  $C_{trough}$  (plasma concentration at the end of the dosing interval) of unchanged edaravone, sulfate conjugate, and glucuronide conjugate for each day of dosing to those after the last dose will be calculated for each subject in Part 2, and the geometric mean and 95% confidence interval will also be calculated.
- The linearity factor (LF) will be calculated to assess the linearity of unchanged edaravone, sulfate conjugate, and glucuronide conjugate after multiple doses in Part 2.

$LF = AUC_{0-T} \text{ (last dose)} / AUC_{0-\infty} \text{ (first dose)}$

T: Dosing interval

- The ratio of accumulation (RA) will be calculated to assess the accumulation of unchanged edaravone, sulfate conjugate, and glucuronide conjugate after multiple doses in Part 2.

$RA = AUC_{0-T} \text{ (last dose)} / AUC_{0-T} \text{ (first dose)}$

T: Dosing interval

(4) Pharmacodynamic assessment

For PD assessments, the Statistical Analysis Plan and report will be prepared separately.

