##### (1) Part 1 (single-dose study)

A single oral dose of the study drug will be given to subjects under fasting conditions in the morning or 30 minutes after breakfast. In Cohort S3-2, subjects in Cohort S3-1 will be given the same study drug that is allocated in Cohort S3-1 in a single oral dose after at least a 4-day washout period. Doses of Cohort S2 and thereafter are tentative. Based on the PK data obtained up to 24 hours post-dose and the safety data obtained up to 48 hours post-dose of the previous cohort, the sponsor and a medical expert will examine and determine the dose with the agreement of the investigator, such that the exposure of the minimum toxic dose (10,226 ng/mL for  $C_{max}$  and 1,226 ng•hr/mL for  $AUC_{0-24hr}$  in a free base form) is not exceeded. However, the highest dose in Part 1 shall not exceed 7,200 mg. The common ratio between the dose and the estimated mean  $C_{max}$  and  $AUC_{0-24hr}$  should be  $\leq 5$  between successive cohorts.

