**Table 2 Dose, Dosing Regimen, and Duration (Multiple-dose study [Part 2])**

Cohort	Dose	Frequency of administration	Duration	No. of subjects	
				Edaravone	Placebo
M1	800 mg/day 	Once daily	5, 9, or 14 days 	6	3
M2	2,400 mg/day 	Once daily or twice daily 	5, 9, or 14 days 	6	3

- 1) The dose and duration for Cohorts M1 and M2, and the frequency of administration for Cohort M2 are tentative.
- 2) The dose and duration for Cohort M1 will be determined based on the PK and safety data collected up to Cohort S4.
- 3) The dose, frequency and duration for Cohort M2 will be determined based on the PK and safety data collected up to Cohorts S6 and M1.

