#### 9.2.4.2 Laboratory Tests

The following laboratory tests will be performed at the time points shown in the table below. If blood sampling and a 12-lead ECG or vital sign measurement are scheduled at the same time point, blood will be drawn after the 12-lead ECG or vital sign (except for body temperature) measurement. The investigator (or subinvestigator) will record the results in the CRF.

The approximate blood volume per sampling is 2 mL for 1), 6 mL for 2), and 1.8 mL for 3), described below.

- 1) Hematology: Hemoglobin, hematocrit, RBC count, WBC count, platelet count, MCH, MCHC, MCV, differential white blood cell count
- 2) Biochemistry: Na, K, Cl, Ca, inorganic phosphorous, urea nitrogen, creatinine, uric acid, total bilirubin, direct bilirubin, ALT, AST, γ-GTP, ALP, LDH, CK, amylase, total cholesterol, triglyceride, LDL-C, HDL-C, total protein, albumin, glucose
- 3) Coagulation test: Prothrombin time, activated partial thromboplastin time
- 4) Urinalysis: Sediment, qualitative analysis (pH, specific gravity, protein, glucose, occult blood, urobilinogen, bilirubin, ketone body)

Part 1 (single-dose study)	Part 2 (multiple-dose study)

• Screening

• Day –1 (hospitalization)*1

• Day 2: Before breakfast

• End-of-study assessment

	

• Screening

• Day –1 (hospitalization)*1

• Day X*2: Before breakfast (pre-dose)

• End-of-study assessment

\* On Day –1 (hospitalization), the assessment will be performed based on results that can be confirmed within the same day.

\* When X = 5 (5-day administration), Days 3 and 6.

When X = 9 (9-day administration), Days 3, 7, and 10.

When X = 14 (14-day administration), Days 3, 7, 11, and 15.

The sponsor will calculate the estimated glomerular filtration rate (eGFR) from creatinine, using the most recent body weight.

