#### 9.2.4.6 Adverse Events

An adverse event (AE) is any untoward medical occurrence or unintended sign (including an abnormal laboratory finding), symptoms, and disease in a patient or subject who is administered a pharmaceutical product during safety evaluation period, and which does not necessarily need to have a causal relationship with the treatment.

The investigator (or subinvestigator) will assess AEs that occur in the subjects from the start of study drug administration to the end-of-study assessment and record the results in the CRF.

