The investigator (or subinvestigator) will assess whether any "reasonable relationship" exists between an AE and the study drug. The assessment will include such factors as the natural course of complications or underlying diseases, combination therapies, risk factors other than the study drug, and the temporal relationship of the event onset to the study drug administration (e.g., recurrence of the event after reintroduction of the study drug, disappearance of the event after discontinuation of the study drug). An AE that is judged as "reasonably related" to the study drug is defined as an ADR.

1. Reasonably related
2. Not reasonably related

5) Outcome

The outcome of AEs will be graded on the following 6-point scale.

1. Recovered
2. Recovering
3. Not recovered
4. Recovered with sequelae

5. Death
6. Unknown

6) Date of outcome

The date of outcome will be defined according to the outcome, as shown below.

Recovered: The date on which a subject has recovered. If the date of recovery cannot be determined, the date of confirmation or judgment of recovery will be used.

Recovering: The date of confirmation or judgment of recovering

Not recovered: The date of confirmation or judgment of not recovered

[figure not shown]
Recovered with sequelae: The date of confirmation or judgment of recovered with sequelae

Death: The date of death. If the date of death cannot be determined, the date of confirmation or judgment of death will be used.

Unknown: If the date of outcome cannot be determined due to the subject's death from a cause other than the AE, the date of death will be used. For other cases, the date of confirmation or judgment will be used.

During hospitalization in this study, the time of outcome will also be determined according to the above criteria. If the time of outcome cannot be determined, the time of confirmation of the outcome will be used.

7) Follow-up

- Period (1) consists of 7 days starting from the day after last dose. During Period (1), AEs will be assessed.
- Period (2) consists of  $\geq 7$  days starting from the day after completion of the end-of-study assessment. During Period (2), AEs that occur during the assessment period (dosing period + [1]) will be followed up.
- The courses of AEs that are followed up during Period (2) will be recorded in the CRF.
- The date of outcome for AEs that are recovering or not recovered will be the date of the last observation in Period (2), which will be recorded in the CRF.

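### Adverse event incidence is compared with pooled placebo although observation windows can differ between pooled cohorts, so a difference can arise without any drug effect

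*Protocol*

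**What the plan says.** Section 13.4 sets the comparison for both parts: "data collected at each dose of each cohort will be compared with the corresponding pooled data of the placebo group". For adverse events it adds that "the number of subjects with TEAEs and the incidence and number of TEAEs will be summarized". It states no person-time denominator, common cut-off or matching of placebo by duration.

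The collection window follows from section 9.2.4.6. The investigator "will assess AEs that occur in the subjects from the start of study drug administration to the end-of-study assessment", and the follow-up rules there say that "Period (1) consists of 7 days starting from the day after last dose". The schedules in section 9.1 put the Part 2 end-of-study assessment on Day 12, 16 or 21, each ±2 days, for 5, 9 or 14 days of dosing.

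Table 2 in section 8.3.1 lists those three durations for each multiple-dose cohort, and "The dose and duration for Cohorts M1 and M2, and the frequency of administration for Cohort M2 are tentative". The M1 duration is set on data up to Cohort S4. For the other cohort, "The dose, frequency and duration for Cohort M2 will be determined based on the PK and safety data" collected up to S6 and M1. Nothing requires the two durations to agree.

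In Part 1, subjects of S3-1 receive the S3-2 dose "in a single oral dose after at least a 4-day washout period". Section 9.1 allows the S3-2 admission assessment to stand in for the S3-1 end-of-study visit.

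**The concern.** Crude incidence grows with time at risk. A placebo pool that mixes windows has an expected incidence belonging to none of its cohorts. Part 2 has 3 placebo subjects per cohort, so if M1 and M2 run for different durations, half of the pool of 6 has the wrong window for each active group. The shorter cohort then tends to look better than placebo and the longer one worse.

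Safety and tolerability are part of the primary objective, and this is the stated safety comparison. M2 has the higher tentative dose, so a longer M2 would lean towards an apparent dose trend and a shorter M2 would tend to hide one.

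**Working it through.** **Design figures.** Section 6.1 gives 74 subjects: 7 × 8 + 2 × 9 = 56 + 18 = 74, reproduced. Dosing duration plus 7 days gives 5 + 7 = 12, 9 + 7 = 16 and 14 + 7 = 21, matching the nominal end-of-study days in section 9.1.

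**Assumptions.** The documents give no adverse event rate, so background risk is assumed and shown as a range. The hazard is constant and there is no drug effect. Section 13.4 does not define which placebo data correspond to which cohort; pooling within each part is assumed. Windows are nominal and ignore the ±2 days.

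**Part 2, 5 versus 14 days of dosing.** With 12-day risk p12, the 21-day risk is p21 = 1 − (1 − p12)^(21/12). The pool of 3 + 3 has expected incidence (p12 + p21)/2, so each cohort is off by (p21 − p12)/2. The standard error (SE) of a 6 versus 6 difference is √(2 × pool × (1 − pool)/6).

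| p12 | p21 | Pool | Shorter cohort − pool | Longer cohort − pool | SE |
|---|---|---|---|---|---|
| 10% | 16.8% | 13.4% | −3 points | +3 points | 20 points |
| 20% | 32.3% | 26.2% | −6 points | +6 points | 25 points |
| 30% | 46.4% | 38.2% | −8 points | +8 points | 28 points |
| 50% | 70.3% | 60.1% | −10 points | +10 points | 28 points |

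**Part 2, less extreme pairs, at a 12-day risk of 20%.** The 16-day risk is 1 − 0.8^(16/12) = 25.7%.
- 5 versus 9 days: (25.7 − 20.0)/2 = 2.9 points each way.
- 9 versus 14 days: (32.3 − 25.7)/2 = 3.3 points each way.
- Equal durations: 0.

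**Part 1, S3-1 at its minimum.** The washout is at least 96 hours, so the shortest S3-1 window is about 4 days. The full Part 1 window is taken as 8 days (dose day plus the 7-day Period 1). This is an assumption, because the end-of-study column of that schedule is not legible in the text at hand. Counted per exposure, the pool holds 14 placebo exposures at 8 days (six other cohorts × 2, plus S3-2 × 2) and 2 at 4 days. With 8-day risk p8, the 4-day risk is p4 = 1 − (1 − p8)^(4/8), and the pool is (14 × p8 + 2 × p4)/16.

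| p8 | p4 | Pool | S3-1 − pool | Other Part 1 cohorts − pool |
|---|---|---|---|---|
| 10% | 5.1% | 9.4% | −4.3 points | +0.6 points |
| 20% | 10.6% | 18.8% | −8.3 points | +1.2 points |
| 30% | 16.3% | 28.3% | −12.0 points | +1.7 points |
| 50% | 29.3% | 47.4% | −18.1 points | +2.6 points |

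The standard error of the S3-1 contrast (6 versus 16 exposures, √(pool × (1 − pool) × (1/6 + 1/16))) runs from 14 to 24 points.

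**The case against.** The strongest reply is that this belongs to the statistical analysis plan, which is not shown. Section 13.1 sends detailed procedures there, section 13.3 does the same for the handling of safety data, and by then the durations will be known. Nothing in section 13.4 forbids a common window. That argues for a light fix but does not remove the point. The pooled comparison and the crude measure are stated in the protocol itself, and section 13.5 asks for a documented reason if they change.

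A second reply is practical, and it stands. No test of adverse event incidence is planned, section 6.1 disclaims a power calculation, and the shift is smaller than the sampling error. Every event is also listed by subject with its timing, so a late event can be recognised as late.

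Two stronger readings are tempting. A reader might infer that incidence will differ from pooled placebo. The documents do not support that: durations are tentative and may coincide, the washout is a minimum, and replacing the S3-1 end-of-study visit is optional.

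A reader might also infer that laboratory and sensory comparisons are distorted, since laboratory days vary with duration ("When X = 14 (14-day administration), Days 3, 7, 11, and 15", against Days 3 and 6 for 5-day dosing). But section 13.4 summarises laboratory values by time point. The last in-house laboratory day (6, 10 or 15) is always the day after the last dose, and so is the post-dose sensory test. Those visits already align by time since last dose.

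**Conclusion.** The point holds conditionally and is minor. A rule stated in section 13.4 can produce a difference from pooled placebo without a drug effect if M1 and M2 receive different durations or if S3-1 is shortened. In Part 2 the size is about 3 to 10 points each way in the most unequal case and about 3 points for the adjacent durations at a 20% 12-day risk. In Part 1 it is about 4 to 18 points for S3-1 at its minimum window and under 3 points for the other cohorts. If windows are equal it is zero.

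These figures rest on assumed event rates, a constant hazard, pooling within each part and an 8-day Part 1 window. The documents do not support a claim that the safety conclusions would be overturned. The case for acting is that the shift is systematic, concerns a primary-objective comparison and is cheap to remove.

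**What to change.** Add to section 13.4(2), or record as a documented change in the statistical analysis plan before data lock:

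- Where windows differ between pooled cohorts, tabulate TEAEs against pooled placebo over the window common to those cohorts, counted from first dose.
- Beside it, show the full window with placebo by duration (own cohort) and events per subject-day.
- If S3-1 is shortened, compare it with pooled placebo over the same post-dose interval, and state how the S3-1 and S3-2 placebo exposures are counted.

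No change is needed for laboratory or sensory results. The cost is wording and one extra table per part. Own-cohort placebo columns are small (n = 2 or 3), and late events in the longer cohort appear only in the full-window table, which is why both tables are needed. Conduct, sample size and dosing are untouched.
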